#### 7.6 Vital Signs

Vital signs (pulse and blood pressure) will be measured at Screening and Check-in for all product arms. For *my*bluTM and continue-smoking arms, the vital signs will also be performed at Day 5 and at Day 28, 29 (Period 1), and in Period 2 on Day 56 and at

the discharge from the study (Day 57) or upon early termination. For JUUL arm, the vital sign will be performed at Day 1 or upon early termination.

Descriptive statistics will be reported for vital sign measurements by product arm and time point. Unscheduled events or rechecks post randomization will not be included in summaries. Similarly early termination results will not be included in summaries.

# 7.7 Electrocardiogram

A single 12-lead electrocardiogram (ECG) will be recorded at Screening for all product arms. For *my*bluTM and continue-smoking arms, the ECG will also be performed at the discharge from the study (Day 57) or upon early termination. For JUUL arm, the ECG will be performed at Day 1 and upon early termination.

Descriptive statistics will be reported for ECG parameters by product arm and time point. Unscheduled events or rechecks post randomization will not be included in summaries. Similarly early termination results will not be included in summaries.

ECG results will be listed by subject.

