6.2.11 Electrocardiogram

12-lead ECGs will be taken following resting in the supine position for at least 5 minutes and at least 15 minutes after the last cigarette smoked or study product used during Screening and at discharge from the study. ECGs will be interpreted, signed, and dated by the Investigator or a qualified designee. Clinic site reference ranges will be applied to all ECG parameters. The ECG machine will compute the PR and QT intervals, QT interval corrected for heart rate using Bazett's (QTcB) formula, QRS duration, and heart rate and this information will be documented in the subject file. The ECGs will be interpreted as normal, having a clinically insignificant abnormality, or having a clinically significant abnormality. The overall interpretation will be noted in the eCRF.

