## Secondary:

- 1. To assess the change-from-baseline differences in the primary tobacco-related BoE following a 56-day use period of *my*bluTM e-cigarettes relative to smoking usual brand combustible cigarettes.
- 2. To assess the change-from-baseline differences in the secondary tobacco-related BoE following 28-day and 56-day use periods of *my*bluTM e-cigarettes relative to smoking usual brand combustible cigarettes.
- 3. To characterize the change in the primary and secondary BoE and biomarkers of potential harm (BoPH) during a 56-day period of use of *my*bluTM e-cigarettes.
- 4. To assess the change-from-baseline differences in the primary and secondary tobaccorelated BoE between Day 28 and Day 56 in subjects using *my*bluTM e-cigarettes.
- 5. To assess change-from-baseline differences in the (BoPH following 28-day and 56-day use periods of *my*bluTM e-cigarettes relative to smoking usual brand combustible cigarettes.
- 6. To assess change-from-baseline differences in physiologic endpoints following 28-day and 56-day use periods of *my*bluTM e-cigarettes relative to smoking usual brand combustible cigarettes.
- 7. To assess elements of abuse liability, subjective effects, and perceptions associated with use of mybluTM e-cigarettes.
- 8. To characterize use of four *my*blu™ e-liquids (Tobacco Chill and Honeymoon flavor Intense e-liquids, 2.5% and 4.0% nicotine) during a 56-day use period.

- 9. To characterize nicotine uptake from the *my*blu™ e-cigarettes relative to an e-cigarette comparator (JUUL® Virginia Tobacco 5% nicotine) and usual brand combustible cigarettes.
- 10. To confirm the safety of mybluTM e-cigarettes during a 56-day use period.

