#### 6.3 Physiologic Assessments

#### **6.3.1** Physiologic Assessments and Visits

Test Visit 1, 3, and 5 check-in blood pressure (systolic and diastolic) and heart rate measurements will be assessed for physiologic assessment purposes.

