### Clinical Study Report No. CA22747

Appendix 16.2.8.3 12-Lead Electrocardiogram (Safety Population)

Page	1	of	Χ
------	---	----	---

							Heart			If Abnormal					
Subject St	-	ECG	Reason for				Rate	PR	QRS	QΤ	QTcB*				
Number Vi	sit	Done?	Not Done	Date	Time	Result	(bpm)	(msec)	(msec)	(msec)	(msec)	Specify	Action Taken		
Y Scr	eenina	XXX			v•xx•xx	Normal		XXX X	XX X	XXX X	XXX X				

Note: QTCB\* = QTc corrected using Bazett's correction.

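### QT is rate-corrected by Bazett's formula only, so a heart-rate difference between Screening and Day 57, or between arms, could appear as a QTc change or hide one; Fridericia's correction should be shown beside it

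*SAP*

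**What the plan says.** Protocol 6.2.11 has the ECG machine compute PR, QT, "QT interval corrected for heart rate using Bazett's (QTcB) formula, QRS duration, and heart rate". Tracings are taken supine after at least 5 minutes' rest and at least 15 minutes after the last cigarette or product use, at Screening and at study discharge.

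SAP 7.7 sets the schedule: "A single 12-lead electrocardiogram (ECG) will be recorded at Screening for all product arms"; for the myblu and continue-smoking arms, "the ECG will also be performed at the discharge from the study (Day 57) or upon early termination". Early-termination tracings are left out of the summaries. The analysis is one sentence, "Descriptive statistics will be reported for ECG parameters by product arm and time point", which names no correction formula. The listing shell, Appendix 16.2.8.3, has columns for heart rate, PR, QRS, QT and QTcB, with the footnote "QTc corrected using Bazett's correction". The SAP lists Table 14.3.5.5 as the ECG summary but gives no shell for it. No second correction appears in either document.

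Heart rate is also a secondary physiologic endpoint. SAP 6.3.1 states that "check-in blood pressure (systolic and diastolic) and heart rate measurements will be assessed for physiologic assessment purposes", and secondary objective 6 is "To assess change-from-baseline differences in physiologic endpoints following 28-day and 56-day use periods of" myblu relative to continued smoking.

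**The concern.** Bazett's formula divides QT by the square root of RR. Where the true dependence is weaker, it over-corrects, and QTcB rises and falls with heart rate. The ECG heart rate therefore needs to be comparable across visits and arms before a QTcB difference can be read as a repolarisation effect. Two features of the plan make that unsafe to assume.

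- The trial tests heart rate for a product effect, so an arm difference is an open question by its own design.
- The two ECGs are taken under different conditions. In the Screening schedule (Protocol Table 4), spirometry follows all the other listed assessments, including the ECG. In the Test Visit 5 schedule (Protocol Table 9), scheduled product use ends at 14:00, spirometry follows FeNO, and the ECG is listed with the discharge events at about 18:00. Spirometry includes albuterol (Protocol 6.2.12). The end-of-use ECG may thus come hours after product use and after a bronchodilator.

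At stake is the reading of the ECG part of secondary objective 10, safety. There is one scheduled tracing before product use and one at the end. If arms differ in QTcB, the planned table cannot say whether repolarisation or heart rate moved.

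**Working it through.** The documents state no QT, QTc or expected heart-rate figure, so there is nothing of the plan's own to reproduce. The calculation shows how far QTcB moves when heart rate alone changes.

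**Inputs from the documents.** Bazett is the only correction; QT and heart rate are both recorded (Protocol 6.2.11; Appendix 16.2.8.3). Eligible heart rate at Screening runs from 40 to 99 bpm (exclusion criterion 8), which bounds the starting rate but does not fix it.

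**Assumptions.** Rate-free QTc, Q = 400 to 410 ms; starting heart rate 65 to 75 bpm; QT-RR exponent k = 1/3 to 0.40, with k = 0.5 as the case in which Bazett is exact; heart-rate shifts of 2 to 5 bpm.

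**Formulas.** With RR = 60/HR and QT = Q × RR^k:
- QTcB = QT/RR^(1/2) = Q × (HR/60)^(1/2 − k)
- QTcF = QT/RR^(1/3) = Q × (HR/60)^(1/3 − k)

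**A 5 bpm fall with no true QTc change**

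| Q (ms) | HR (bpm) | k | QTcB before → after (ms) | Change in QTcB | Change in QTcF |
|---|---|---|---|---|---|
| 410 | 65 → 60 | 1/3 | 415.5 → 410.0 | −5.5 | 0 |
| 410 | 70 → 65 | 1/3 | 420.7 → 415.5 | −5.2 | 0 |
| 400 | 75 → 70 | 1/3 | 415.2 → 410.4 | −4.7 | 0 |
| 410 | 70 → 65 | 0.40 | 416.4 → 413.3 | −3.1 | +2.0 |
| 400 | 75 → 70 | 0.40 | 409.0 → 406.2 | −2.8 | +1.8 |
| 400 | 75 → 70 | 0.50 | 400.0 → 400.0 | 0 | +4.5 |

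Over the assumed grid the QTcB artefact runs from −5.5 to −2.8 ms for k between 1/3 and 0.40. At k = 0.5 the error passes to Fridericia: for Q = 400 ms and 75 → 70 bpm, QTcF goes from 400 × (75/60)^(−1/6) = 385.4 to 400 × (70/60)^(−1/6) = 389.9 ms, or +4.5 ms.

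**Smaller shifts.** A 2 bpm fall gives −1.1 ms (Q = 400, 75 bpm, k = 0.40) to −2.2 ms (Q = 410, 65 bpm, k = 1/3). A 3 bpm fall gives −1.7 to −3.3 ms at the same corners.

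**Masking.** Take Q = 400 ms, k = 1/3, a true rise of 5 ms and a fall from 75 to 70 bpm. QTcB goes from 415.2 to 405 × (70/60)^(1/6) = 415.5 ms, so the 5 ms rise shows as +0.4 ms (from unrounded values).

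**The case against.** The strongest reply has four parts.

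- **Every input to the size is assumed.** The documents do not say whether, how far or in which direction heart rate will move, or what the QT-RR exponent is. This stands, and it makes the point conditional. A reader might infer that QTcB will be off by several milliseconds; the documents do not support that. A 2 to 3 bpm shift gives at most about 2 to 3 ms, and at exponent 0.5 there is no Bazett artefact. For the same reason the documents do not support making QTcF the lead variable.
- **The heart-rate endpoint is not the ECG heart rate.** The endpoint comes from seated vital signs at check-in for Test Visits 1, 3 and 5; the ECG rate is supine, at Screening and discharge. This stands in part. A seated effect would not prove a supine one, but the different conditions of the two ECGs are a separate reason for doubt. That reason is not certain either: discharge events may be done earlier than 18:00, and Protocol 6.3.1 allows product use after the urine collection if time permits.
- **The information is already there.** Heart rate, QT and QTcB stand side by side in the listing, and heart rate may well be among the summarised parameters. This is true of the data. Yet readers will use the summary table, and mean QTcB with mean heart rate does not yield mean QTcF.
- **Nothing turns on QTc.** No QTc hypothesis, threshold or decision rule is planned. Each tracing is also read for clinical significance, and safety rests on several other assessments. This stands and sets the severity.

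**Conclusion.** The point holds as a minor, conditional gap in the planned summary; the necessary data are being collected. Bazett is the only correction reported, and equal ECG heart rate at Screening and Day 57, or across arms, cannot be taken for granted. If heart rate falls by 5 bpm, QTcB could shift by about -5.5 to -2.8 ms with no repolarisation change, assuming a rate-free QTc of 400 to 410 ms, a start of 65 to 75 bpm and an exponent of 1/3 to 0.40. The exponent and the heart-rate shift are the assumptions that matter most, and the documents supply neither. Since each formula is exact at a different exponent, the supportable conclusion is to show both. A reader might go further and infer that the safety objective fails or that a primary result is affected; neither follows, because the ECG is one descriptive item among several safety assessments.

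**What to change.** In SAP 7.7, define QTcF = QT/(60/HR)^(1/3), with QT in ms and HR in bpm, from the QT and heart rate on the same tracing. Name the parameters to be summarised. In Table 14.3.5.5 show QTcF beside QTcB, QT and heart rate by arm and time point, and add a QTcF column to Appendix 16.2.8.3. If the two corrections agree, a rate artefact is unlikely to explain what is seen; if they part, the heart-rate row shows where to look.

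The cost is one more derived variable to program and interpret, with one added table entry and one listing column. No new procedure or data collection is needed.

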#### 7.8 Concomitant Medications

All concomitant medications recorded during the study will be coded with the WHO Drug Dictionary Version 01MAR2018 and listed by subject.

#### 7.9 Physical Examination

Full physical examinations will be performed at Screening. For *my*blu™ and continue-smoking arms, symptom driven physical examination will also be performed at Check-in (Day -2), Test Visit 1 discharge (Day 5) and at Day 28, 29 of Period 1, Day 56 of Period 2 and the discharge from the study (Day 57) or upon early termination. For JUUL arm, the symptom driven physical examination will be performed at Check-in (Day -2) and Day 1 or upon early termination.

Physical examinations will be listed by subject. Changes in physical examinations (if any) will be described in the text of the final report.

#### 7.10 Exhaled CO

Exhaled CO will be collected at Screening and Check-in (Day -2) for all product arms. For *my*bluTM and continue-smoking arms, exhaled CO will also be performed at Test Visit 1 discharge (Day 5) and at Day 28, 29 of Period 1, Day 56 of Period 2.

Descriptive statistics will be reported for exhaled CO by product arm and time point. Unscheduled events or rechecks post randomization will not be included in summaries. Similarly early termination results will not be included in summaries.

Exhaled CO will be listed by subject.

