Product Use ¹¹			х				X												
Pod Weight Documentation ⁷							X												
Blood Sampling ¹²			Х				Х												
Urge to Smoke Assessments 13			Х				Х												

- ¹ Discharge from Test Visit 1 will be as follows. Day -1: Subjects in the continue-smoking arm who do not participate in the PK. Day 1: Subjects in the continue-smoking arm who participate in the PK assessment. Day 3: Subjects in the *my*bluTM arm who do not participate in the PK assessment. Day 5: Subjects in the *my*bluTM arm participating in the PK assessment.
- ² The clinic staff will make a telephone call within 24 48 hours prior to the scheduled visits to remind subjects of the date and time of the upcoming Test Visits.
- ³ Updated as necessary.
- ⁴ Study discharge/early termination events.
- ⁵ mybluTM arm only.
- ⁶ All subjects will smoke their usual brand combustible cigarettes prior to Day 1 and will use study product according to the randomization from Day 1 through discharge from the study.
- ⁷ Pods used during the 24-hour urine collections and PK sessions will be weighed prior to and following use.
- ⁸ Subjects will be trained on use of the ambulatory product use reporting system.
- ⁹ Collections for selected BoE, nicotine equivalents, and questionnaires for *my*bluTM subjects who participate in the PK sub-study.
- ¹⁰ Continue-smoking arm on Day 1, *my*bluTM arm on Day 5.
- ¹¹ Two product use sessions: fixed puffing regimen in the morning and an ad libitum regimen in the afternoon.
- ¹² Blood samples for nicotine concentration measurement will take place approximately 5 minutes prior to and at 3, 5, 7, 10, 12, 15, 20, 30, 60, 120 and 180 minutes following the start of each product use episode (Day 1 continue-smoking, Day 5 *my*bluTM).
- ¹³ Urge to smoke assessments will take place approximately 10 minutes prior to and within approximately 30 seconds prior to the scheduled blood draws at 5, 10, 15, 30, 60, and 120 minutes following the start of the *ad libitum* product use sessions.
- ¹⁴ At the discretion of the site, Test Visit 3 and Test Visit 5 may be ambulatory and subjects may complete selected procedures at home (e.g., 24-hour urine collection, completion of questionnaires). Subjects will be provided the materials required to complete the selected procedures and will be instructed on at-home procedures (e.g., urine collection method, questionnaires).

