Following discharge from Test Visit 1, subjects in the *my*bluTM and continue-smoking arms will follow the product use requirements of their randomization arm and will report product use daily. All subjects in the *my*bluTM and continue-smoking arms will be required to present to the clinic site on Day 14 and Day 28 (each ± 2 days) for Test Visits 2 and 3, respectively. Reminder phone calls will be made to the subjects 24 to 48 hours prior to each test visit. Test Visit 2 will be ambulatory and primarily for the return and dispensing of test products for the *my*bluTM arm and for compliance and safety checks for both study arms. Test Visit 3 will be for these purposes in addition to completion of the endpoint assessments during confinement. At the discretion of the site, Test Visit 3 (i.e., Days 28 and 29) may be ambulatory and selected procedures may be performed by subjects at home (e.g., 24-hour urine collection, completion of questionnaires). Subjects will be provided the materials required to complete the selected procedures and will be instructed on at-home procedures (e.g., urine collection method, questionnaires).

Time	Procedures	Comments
	Document AEs and medications	
	Urine sample for cotinine and pregnancy (females) tests	Female subjects must have a negative pregnancy test prior to product dispensing
	Exhaled CO measurement	Exhaled CO should be measured within 1 hour of check-in.
	Document non-compliant tobacco product use and update usual brand cigarette documentation	
	Review of tobacco and nicotine restrictions	
	Test product collection/dispensing	
	Subject product use reporting confirmation	

Table 6Test Visit 2 Schedule

Table 7Test Visit 3 Schedule

Time*	Procedures	Comments
Day 28		
	Check-in events	
	my blu™ product return and combustible cigarette check-in	
	Urine collection for urinalysis, cotinine, and pregnancy (females) tests	Female subjects must have a negative pregnancy test prior to completing the remaining assessments.
	Exhaled CO measurement	Exhaled CO should be measured within 1 hour of check-in.
	Vital signs	Subjects must be seated for at least 5 minutes prior to measurement, must be collected at least 15 minutes after the last study product used.
	Document non-compliant tobacco product use and update usual brand cigarette documentation	
	Update AEs and medications	Throughout the day
	Symptom-driven physical examination	

Time*	Procedures	Comments
	Body weight documentation	

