6.3.3 Product Use Compliance

Subject compliance with study product use and reporting is a critical component of this study, though 100% compliance from all subjects is an unrealistic expectation. Subjects in the *my*bluTM arm will be reminded at each dispensing for ambulatory use that they are expected to exclusively use the test products without dual use of combustible cigarettes, but that they should be honest about smoking combustible cigarettes as the laboratory assessments will detect use of these products.

Subject self-reported product use will be used as a measure of compliance. The clinic staff will monitor the frequency with which subjects complete the daily product use entries leading up to each Test Visits 2 through 5 and will discuss with subjects any concerns about the entries (e.g., missed reporting, significantly abnormal product use entries). Subjects who complete the daily product use entries on less than 70% of the study days prior to a test visit will be reminded of the importance of documenting product use. Subjects who continue to regularly fail to complete the daily product use entries may be identified by the Investigator as individuals whose noncompliance may jeopardize the integrity of the study data. Disqualification for noncompliance with these product use requirements may only occur in consultation with the Sponsor.

As solely relying on self-reported product use may lead to a conclusion of a higher rate of compliance than actually occurred, biochemical verification of compliance will also be used. While it is recognized that there are many other potential sources of CO and nicotine exposure, exhaled CO and urine cotinine will be used as methods of verifying compliance in real-time. Subjects with values inconsistent with their randomization arm (i.e., subjects in the *my*bluTM arm with exhaled CO values > 8 ppm or negative urine cotinine tests, subjects in the continue-smoking arm with exhaled CO values < 10 ppm or negative urine cotinine tests) will be questioned regarding their recent product use and any information provided will be documented in the subject file. Subjects will be reminded of the importance of compliance

with study instructions, including accurate reporting of other nicotine and tobacco products used.

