7.2.2 Intent-to-Treat Population

The ITT population will consist of randomized subjects with at least one documented product-use experience from Day 1, irrespective of their compliance of the product-use to which they were randomized.

7.2.3 **Per-Protocol Population**

The PP population is a subset of the ITT population who meet the requirements below. Separate populations for Product Use Periods 1 and 2 will be established based on data collected during each of those periods.

*my*bluTM and continue-smoking arms

- Have no protocol deviations significantly impacting the integrity of the analysis or interpretation of the individual endpoint under consideration (e.g., compromised urine samples, use of prohibited medications impacting the endpoint)
- Have a daily product use response rate of at least 70% during the product use period
- Have a positive urine cotinine test at each scheduled assessment

mybluTM arm

- Self-report reducing cigarette consumption by at least 90% of that reported at baseline
- Have exhaled CO values ≤ 8 ppm at each scheduled post-baseline assessment
- Have post-baseline urine NNAL values reduced by \geq 75% from baseline

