#### Compliance

- $\geq$  90% reduction of cigarette use from baseline (*my*bluTM arm)
- $\geq 70\%$  daily product use reporting (yes/no) all cohorts
- Measured eCO (≤8 ppm) all cohorts
- $\geq 75\%$  reduction in post-baseline urine NNAL from baseline (*my*bluTM arm)
- Urine cotinine (yes/no) all cohorts

All product use data (including the number of puffs and including the PK product use sessions) and compliance variables will be summarized by study product using descriptive statistics (by time point, day, and product use session as appropriate) but no statistical comparisons will be made. The difference in weight before and after use of each e-cigarette (Products A to D and Product F) will be summarized.

For the PK sub-study, the number of puffs and the difference in weight before and after use of each e-cigarette will also be summarized.

The level of precision for each statistic will be presented as follows:

- minimum/maximum in same precision as the data,
- arithmetic mean/median in one more level of precision than minimum/maximum,
- SD in one more level of precision than mean/median,
- n will be presented as an integer,
- arithmetic CV% will be presented to 1 decimal point, and

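### SAP 7.10 gives exhaled CO days that contradict protocol Table 2, and the SAP 6.1.2 8 ppm compliance item reverses the protocol's check for continuing smokers

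*SAP*

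**What the plan says.** **Schedule.** The protocol's exhaled CO row in Table 2 marks Day -2, Test Visit 1 discharge, and Days 14, 28, 42 and 56. Footnote 5 restricts the discharge measurement: "mybluTM arm only". Footnote 1 puts myblu discharge on Day 3 for subjects outside the PK sub-study and on Day 5 for those in it. Continue-smoking subjects leave on Day -1 or Day 1. Tables 6 to 9 repeat the check at Test Visits 2 to 5, each with the comment "Exhaled CO should be measured within 1 hour of check-in". The Day 29 list in Table 7 has no CO measurement.

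SAP 7.10 says, for the myblu and continue-smoking arms together, that "exhaled CO will also be performed at Test Visit 1 discharge (Day 5) and at Day 28, 29 of Period 1", followed by "Day 56 of Period 2". It then promises that "Descriptive statistics will be reported for exhaled CO by product arm and time point".

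**Cut-off.** Protocol 6.3.3 flags myblu subjects above 8 ppm and, in the other direction, "subjects in the continue-smoking arm with exhaled CO values < 10 ppm or negative urine cotinine tests". The compliance list in SAP 6.1.2 has the single item "Measured eCO (≤8 ppm) all cohorts".

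**PP rule.** Protocol 7.2.3, under the myblu arm only, requires that subjects "Have exhaled CO values ≤ 8 ppm at each scheduled post-baseline assessment". SAP 4.1.3 carries the same criterion with the same arm restriction and names no days.

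**The concern.** Exhaled CO is one of the two real-time biochemical checks on product use. Protocol 6.3.3 justifies such checks by noting that self-report alone may overstate compliance. A SAP that omits Days 14 and 42 leaves collected data out of the planned CO summaries. A compliance item that points the wrong way for smokers would give a misleading rate for the control arm. SAP 7.10 is also the only place in the SAP that lists days for exhaled CO. Someone programming the PP criterion, which refers to scheduled assessments without naming them, could look them up there. PP is the supportive population for the four primary biomarkers and is also used for the product use tables.

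**Working it through.** The plan gives no figure to reproduce on this point, so the check sets the two schedules and the two cut-offs side by side.

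**Schedules after baseline**

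| Assessment | Protocol Table 2 and Tables 5 to 9 | SAP 7.10 |
|---|---|---|
| Test Visit 1 discharge | myblu only; Day 3 (non-PK) or Day 5 (PK) | both arms; Day 5 |
| Day 14 | yes | absent |
| Day 28 | yes | yes |
| Day 29 | no | listed |
| Day 42 | yes | absent |
| Day 56 | yes | yes |

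Of the four post-discharge checks (Days 14, 28, 42, 56), SAP 7.10 keeps two. It adds Day 29, when none is scheduled, and a Day 5 value for smokers, who have already left the clinic.

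**Likely source of the slip.** SAP 7.9, on physical examination, uses the same sequence of discharge on Day 5, then Days 28, 29 and 56. There, Days 28, 29 and 56 agree with Table 2. For urine cotinine, the companion check, SAP 7.5 refers to the first day of each test visit, which keeps Days 14 and 42. SAP section 8 declares no departure from the protocol. This looks like carried-over text rather than a decision.

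**Cut-off in the continue-smoking arm**

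| Exhaled CO | SAP 6.1.2 item, scored as pass/fail | Protocol 6.3.3 |
|---|---|---|
| 8 ppm or less | compliant | inconsistent with arm |
| above 8 and below 10 ppm | not compliant | inconsistent with arm |
| 10 ppm or more | not compliant | consistent with arm |

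The two rules agree only in the band between 8 and 10 ppm and are opposite everywhere else. Inclusion criterion 4 requires CO above 10 ppm at Screening and at check-in for Test Visit 1, so every eligible subject starts in the bottom row.

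**PP membership, conditional illustration.** Suppose the myblu PP criterion were programmed from SAP 7.10, with Day 29 ignored because nothing is collected. Period 1 would then have 2 checks (discharge, Day 28) instead of 3 (discharge, Days 14 and 28). Period 2 would have 1 (Day 56) instead of 2 (Days 42 and 56). If each check is passed independently with probability p, the share passing k checks is p^k. The documents give no pass rate, so p is an assumption, shown over a range.

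| p | Period 1, protocol (p^3) | Period 1, SAP 7.10 (p^2) | Period 2, protocol (p^2) | Period 2, SAP 7.10 (p) |
|---|---|---|---|---|
| 0.70 | 0.343 | 0.490 | 0.490 | 0.700 |
| 0.80 | 0.512 | 0.640 | 0.640 | 0.800 |
| 0.90 | 0.729 | 0.810 | 0.810 | 0.900 |
| 0.95 | 0.857 | 0.902 | 0.902 | 0.950 |

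These shares concern the CO criterion alone, before the other PP criteria. Checks on the same person are probably positively correlated, which would narrow the gaps; if everyone passed all checks or none, the gap would be zero. The table shows the direction and does not estimate the effect.

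**The case against.** The strongest reply is that SAP 7.10 does not define PP. It is in the safety section, promises descriptive statistics and a listing, and does not mention PP. The PP criterion is in SAP 4.1.3, matches the protocol and does not refer to 7.10. SAP section 3 keeps Days 14, 28, 42 and 56 as visits with compliance checks, and SAP 6.1.1 names exhaled CO as a real-time compliance measure, so the scheduled assessments can be read as the protocol's visits. This stands. A reader might infer from the schedule conflict that PP membership is misclassified, but the documents show only an ambiguity that could lead there.

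A reader might also infer that 7.10 admits dual users to PP. Its list does not do so as written: taken literally it requires a Day 29 value that no one has, which would leave no myblu subject eligible. It becomes more lenient only if Day 29 is dropped. Even then, PP still requires at least a 90% self-reported reduction in cigarettes, at least a 75% fall in NNAL and 70% diary reporting.

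On the cut-off, it can be said that the item feeds descriptive summaries only, that SAP section 9 lists no compliance-rate or exhaled CO summary table, and that the protocol uses the word cohort for the four e-liquid groups. The first two points limit the impact. The third does not rescue the wording. In the same SAP list the cigarette-reduction and NNAL items are marked for the myblu arm, while diary reporting and cotinine, which apply to both arms in the PP rule, are marked for all cohorts. As written, the term includes smokers.

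**Conclusion.** The point holds as a contradiction between SAP and protocol, and it is minor. Followed as written, the CO summaries omit two collected visits (Days 14 and 42), call for a Day 29 value and a smokers' Day 5 value that do not exist, and misstate the discharge day for non-PK myblu subjects. If the 8 ppm item is scored as pass/fail, the smokers' CO compliance rate is inverted except between 8 and 10 ppm.

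Misclassification in the myblu PP set is a risk that depends on SAP 4.1.3 being programmed from 7.10, and its size cannot be derived from the documents. The 8 ppm item changes no smoker's PP status, because the PP criterion on CO applies to the myblu arm only in both documents. The primary Day 28 analysis uses the ITT population and is untouched.

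**What to change.** Make three wording changes in the SAP:

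- **7.10:** replace the days and arms with those of protocol Table 2, that is, Test Visit 1 discharge (Day 3 or 5) for the myblu arm only, and Days 14, 28, 42 and 56 for both main-study arms. Delete Day 29.
- **4.1.3:** name the CO visits that count: Test Visit 1 discharge, Day 14 and Day 28 for PP28/29; Days 42 and 56 for PP56/57.
- **6.1.2:** limit the 8 ppm item to the myblu cohorts, and summarise continue-smoking subjects by the protocol 6.3.3 criterion (below 10 ppm is inconsistent with the arm).

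The protocol already schedules all the measurements needed, so no new data are required. The only downside is that PP may be slightly smaller than if it were programmed from 7.10.
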